2.3 Overview of Clinical Studies

Lirentelimab IV, administered as a monthly intravenous infusion, has previously been tested in over 700 healthy volunteers and in subjects with indolent systemic mastocytosis (ISM), chronic urticaria (CU), severe allergic conjunctivitis (AC), mast cell gastritis, eosinophilic gastritis (EG) and/or eosinophilic duodenitis (EoD), and eosinophilic esophagitis (EoE). Multiple monthly doses of 3 mg/kg have been given to subjects with ISM, CU, severe AC, EG and/or EoD, and EoE.

In general, lirentelimab IV has been well tolerated. The most common treatment-emergent adverse events (TEAE) observed with IV infusion were mild to moderate infusion-related reactions (IRR). The IRR were mostly mild to moderate, and occurred most often during the first infusion. IRR that were deemed more serious typically resolved within 24 hours, and additional corticosteroids and/or antihistamines were used in cases when slowing the rate of infusion and additional supportive care alone did not resolve the issue. Common symptoms of IRR were headache, nausea, sweating, flushing, and redness. Most IRR that occurred during the infusion could be managed by slowing or temporary interruption of the infusion, with minimal intervention. In subjects with ISM, CU, severe AC, and EG/EoD, fewer adverse events (AE) including IRR were reported during the second and subsequent infusions when compared to the first infusion. The risk of IRR has been substantially reduced by administration of a single dose of oral corticosteroid (e.g., prednisone 60 mg) given orally 12 to 24 hours prior to the first dose of lirentelimab IV.

Study AK002-017 evaluated the PK and PD of lirentelimab IV and SC in healthy volunteers. Subjects received 0.3, 1, 3, or 5 mg/kg or a fixed dose of 300 mg or 450 mg lirentelimab SC, or 1 mg/kg or 3 mg/kg lirentelimab IV. In each of the SC cohorts, 8 subjects were randomized to lirentelimab (6 per group) or placebo (2 per group) in a double-blind manner; 12 subjects received lirentelimab IV (6 subjects per group) in an open-label manner.

The study showed that the PD effect (depletion of blood eosinophils) occurred within 1 hour of dosing and lasted for at least 1 month at IV and SC doses of 1 mg/kg and for 3 months at all higher IV and SC doses. The SC injections were well tolerated, and no injection site reactions or general injection reactions were noted at any dose demonstrating suitability for further evaluation.

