- Blood for CBC with differential, including absolute blood eosinophil count, will be obtained at screening, just prior to each SC injection, 1 hour (±15 minutes) after the end of each SC injection, and on all follow-up days (14, 56, and 84 [±5] days after last dose if ET). All differential blood counts from Day 1 (post-dose) through the end of the subject's participation in the double-blind period will be blinded to the Sponsor and the site. An unscheduled CBC may be collected at the request of the Safety Monitor. 14)
- Blood for PK will be obtained predose on all dosing days as well as on Day $8 (\pm 3)$ and on follow-up days (14, 56 and 84 ± 5] days after last dose of study drug if ET). 15)
- Blood for ADA will be collected predose on dosing Days 1, 29, and 43, as well as on Day 8 (±3), and on follow-up Days 85 and 155 (14 and 84 [±5] days after last dose of study drug if ET). The ADA sample will also be collected any time an immunogenicity-related AE occurs. 16)
- Urine will be collected for dipstick pregnancy test on all dosing days, Day 8, and all follow-up days (14, 56, and 84 [±5] days after last dose of study drug if ET) for all subjects of childbearing potential. Test kits will be supplied by the central laboratory. Tests will be completed on site and evaluated prior to each SC injection. 17)
- Urine for standard urinalysis will be obtained at screening and on follow-up Days 85 and 155 (14 and 84 [±5] days if ET), and symptom-based, as necessary. 18)
- Randomization will be conducted through the IRT system. Subjects will be randomized 1:1, 300 mg lirentelimab SC or placebo SC. They will be stratified based on biologic status and UAS7 score at baseline. 19)
- The capture of non-serious AE and adverse events of special interest (AESI) will begin after the first dose of study drug has occurred. 20)
- The reporting of serious adverse events (SAE) occurring after signing the ICF and prior to the first SC injection will be limited to those that relate to screening procedures. The capture of all SAE and AE that are not related to screening procedures will begin at the time of first SC injection of study drug.
- Lesional (if available) and nonlesional skin biopsies will be collected at selected US sites and is optional for subjects. Biopsies may be collected at baseline/predose on Day 1 and post-dose on either Day 57, Day 71, or Day 85. See Section 12.1.11. 22)

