14.11 Study Withdrawal Criteria

Participation of a subject will be discontinued in the event that:

- Occurrence of an exclusion criterion, which is clinically relevant and affects the subject's safety, if discontinuation is considered necessary by the Investigator and/or Sponsor.
- Rebounding of eosinophil counts to >1500/mL in subjects who entered the study with eosinophil levels >1500/mL and whose eosinophil counts were initially suppressed after study drug, as assessed by the Safety Monitor, may be withdrawn from the study at the instruction of the Medical Monitor.
- Serum transaminases (ALT and/or AST) >3 × ULN and total bilirubin >2 × ULN (confirmed by subsequent repeat) without an alternative explanation.
- Elevation of ALT or AST >3 × ULN (confirmed by repeat) with the appearance or worsening of symptoms felt by the Investigator to be potentially related to hepatic inflammation, such as fatigue, nausea, vomiting, right upper quadrant pain or tenderness, fever, and rash.

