Definition: A disorder characterize Navigational Note: -	d by a feeling of general disco	mfort or uneasiness, an out-of-so	orts feeling.	,	
Multi-organ failure -		a *	Shock with azotemia and acid-base disturbances; significant coagulation abnormalities	Life-threatening consequences (e.g., vasopressor dependent and oliguric or anuric or ischemic colitis or lactic acidosis)	Death

CTCAE v5.0 - November 27, 2017 Back to TOC Page 42

Figure 4 Example of Grading for General Disorders and Administration Site Conditions

20.6 Appendix 6: Common Terminology Criteria for Adverse Events v. 5.0 cont.

		Investigations			10
CTCAE Term	Grade 1	Grade 2	Grade 3	Grade 4	Grade
Lipase increased	>ULN - 1.5 x ULN	>1.5 - 2.0 x ULN; >2.0 - 5.0 x ULN and asymptomatic	>2.0 - 5.0 x ULN with signs or symptoms; >5.0 x ULN and asymptomatic	>5.0 x ULN and with signs or symptoms	5) S)
	laboratory test results that indica	te an increase in the level of lipa s	e in a biological specimen.		
Navigational Note: -	co.		76	9	
Lymphocyte count decreased	<lln -="" 0.8="" 800="" <lln="" mm3;="" x
10e9/L</lln>	<800 - 500/mm3; <0.8 - 0.5 x 10e9 /L	<500 - 200/mm3; <0.5 - 0.2 x 10e9 /L	<200/mm3; <0.2 x 10e9 /L	2
Definition: A finding based on Navigational Note: -	laboratory test results that indica	te a decrease in number of lymph	ocytes in a blood specimen.		
Lymphocyte count increased		>4000/mm3 - 20,000/mm3	>20,000/mm3		3
Definition: A finding based on Navigational Note: -	laboratory test results that indica	te an abnormal increase in the nu	imber of lymphocytes in the bloo	d, effusions or bone marrow.	
Neutrophil count decreased	<lln -="" 1.5<br="" 1500="" <lln="" mm3;="">x 10e9 /L</lln>	<1500 - 1000/mm3; <1.5 - 1.0 x 10e9 /L	<1000 - 500/mm3; <1.0 - 0.5 x 10e9 /L	<500/mm3; <0.5 x 10e9 /L	2
Definition: A finding based on Navigational Note: -	laboratory test results that indica	te a decrease in number of neutr	ophils in a blood specimen.		18 18
Pancreatic enzymes decreased	<lln and="" asymptomatic<="" td="">Increase in stool frequency, bulk, or odor; steatorrhea	Sequelae of absorption deficiency	HET:	8	</lln>	Increase in stool frequency, bulk, or odor; steatorrhea	Sequelae of absorption deficiency	HET:	8
Definition: A finding based on Navigational Note: -	laboratory test results that indica	te an decrease in levels of pancre	atic enzymes in a biological speci	men.	33

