- If absolute lymphocyte and/or eosinophil counts have not recovered by the OLE Day 155 visit (last follow-up visit), subjects will return approximately every 28 days for extended follow-up until counts have recovered.
- If extended follow-up is required, data collection will be limited to hematology, SAE, and AESI.

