20.9.7 OLE Procedures and Guidelines

The OLE period will be conducted in accordance with Table 10 (Schedule of Assessments: Open-Label Extension Period) and the protocol. This includes prohibited medications, dietary and lifestyle restrictions, study drug preparation and administration, study assessment and procedure guidelines, AE reporting, withdrawal criteria and stopping rules, data collection and management, and ethical and regulatory requirements.

The Investigator will evaluate whether the subject is eligible for the OLE period. On Day 85, eligible subjects that choose to participate in the OLE period will begin following the OLE Schedule of Assessments (Table 10) and will receive the first open-label dose of lirentelimab.

Table 10 Study AK002-027 Schedule of Assessments: Open-Label Extension Period

Assessment/Procedure			OLE Treati	OLE Treatment Period			OLE	OLE Follow-Up Period	riod
Description			M 7I)	(12 weeks)				(12 weeks)	
	OLE Day 1¹6 (±5 days)	OLE Day 15 (±5 days)	OLE Day 29 (±5 days)	OLE Day 43 (±5 days)	OLE Day 57 (±5 days)	OLE Day 71 (±5 days)	OLE Day 85 (±5 days)	OLE Day 127 (±5 days)	OLE Day 155 (±5 days)
	OLE Baseline (Day 85-DB) ¹⁶								
	Week 12 OLE Dose 1	Week 14 OLE Dose 2	Week 16 OLE Dose 3	Week 18 OLE Dose 4	Week 20 OLE Dose 5	Week 22 OLE Dose 6	Week 24 FUP-1	Week 30 FUP-2	Week 34 FUP-3/EOS
Confirm informed consent for OLE	×								
Prior/concomitant medications	X	X	X	X	X	X	X	X	X
Body weight	X	X	X	X	X	X	X	X	X
Vital signs ¹	X	X	X	X	X	X	X	X	X
Symptom-directed physical exam ²	X	X	X	X	X	X	X	X	X
UPDD^3	~>)	Complete daily	from screening	through OLE Da	Complete daily from screening through OLE Day 155 or 84 days post-last dose-	s post-last dose		<
UAS74	X	X	X	X	X	X	X	X	Х
5	X		X		X		X	X	X
⁶ (if applicable)	X	X	X	X	X	X	X	X	X
	X	X	X	X	X	X	X	X	X
Atopic Conditions Questionnaire7	X						X		
Blood for total serum IgE8	X			X		X	X	X	X
Blood for chemistry ⁹	X	X	X	X	X	X	X	X	X
Blood for CBC with differential ¹⁰	X	X	X	X	X	X	X	X	X
Blood for PK ¹¹	X	X	X	X	X	X	X	X	Х
Blood for ADA 12	X			X			X		Х
Urine for dipstick pregnancy ¹³	X	X	X	X	X	X	X	X	X
Urine for urinalysis 14	X						X		X

Assessment/Procedure Description			OLE Treatment Period (12 weeks)	nent Period eeks)			OLI	OLE Follow-Up Period (12 weeks)	riod
	OLE Day 1 ¹⁶ (±5 days) OLE Baseline (Day 85-DB) ¹⁶	OLE Day 15 (±5 days)	OLE Day 29 (±5 days)	OLE Day 43 (±5 days)	OLE Day 57 (±5 days)	OLE Day 71 (±5 days)	OLE Day 85 (±5 days)	OLE Day 127 (±5 days)	OLE Day 155 (±5 days)

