5.1 General Methodology

All statistical analyses will be conducted using SAS v9.4 or later version on the Microsoft Windows Operating System.

All eCRF data (raw data) will be converted into SDTM (Study Data Tabulation Model) datasets, which will be used to create ADaM (Analysis Data Model) data sets. The creation of the SDTM and ADaM data sets will follow the CDISC (Clinical Data Interchange Standards Consortium) standards and the FDA Study Data Technical Conformance Guide. All analysis tables and listings will be created from the ADaM data sets.

Continuous data will be summarized using "n" (number of subjects with non-missing observations), mean, median, standard deviation (SD), minimum value, and maximum value. Categorical data will be summarized using the frequency count and percentage (n, %) of subjects in each category. Number of subjects with non-missing values or number of subjects with missing values (e.g., Not Done) will be presented, where appropriate. Subjects with missing values will not contribute to the denominator for percentage calculations, unless specified otherwise. Counts of 0 in any category will be presented without percentage. All summaries will be presented for individual treatment groups. In Allakos Inc. Page 24 of 49 *Confidential* addition, for summary of disposition and subject baseline characteristics, the presentation will include both treatment groups combined.

The precision rules for the presentation of summary statistics will be:

- Sample size (n, N) and number of missing responses (if displayed): Integer
- Mean, confidence interval, and median: Same number of decimal places as reported/collected
- Standard deviation: Same number of decimal places as reported/collected
- Percentiles, minimum, maximum: Same number of decimal places as reported/collected
- Odds Ratio: 2 decimal places
- Percentage: 1 decimal place generally, or 2 decimal places for <0.1%, or no decimal places for 0% and ≥100%
- P-value: 4 decimal places
- WBC: 2 decimal places as $0.01 \times 10^9/L$
- Height/Weight/BMI: 1 decimal place

The data summaries will be accompanied by individual subject data listings. All data available from questionnaires, eCRF, and external transfer (labs) will be listed and will include relevant subject information, e.g., treatment group and study day. The listings will be sorted in the order of treatment group, subject ID, assessment name and date/time.

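### Protocol 14.11 prints the eosinophil-rebound withdrawal limit per mL, which is 1.5 cells/µL and probably 1,000 times too low (minor)

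*Protocol*

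**What the plan says.** Protocol 14.11 opens its list with "Participation of a subject will be discontinued in the event that". The second item is "Rebounding of eosinophil counts to >1500/mL in subjects who entered the study with eosinophil levels >1500/mL and whose eosinophil counts were initially suppressed"; the suppression meant is the one that follows dosing. The limit of 1500 per mL therefore appears twice, once for the level at entry and once for the level on rebound. The Safety Monitor makes the assessment, and such a subject may then be withdrawn if the Medical Monitor so instructs. No count, percentage fall or time point defines initial suppression.

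Three other places bear on the limit:

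- Table 1, note 14 (Protocol 5.2) shows that the counts are available throughout: "Blood for CBC with differential, including absolute blood eosinophil count, will be obtained at screening, just prior to each SC injection", and again after each injection and at follow-up.
- Protocol Appendix 6, Figure 5, in its neutrophil row, grades counts as "<1500 - 1000/mm3; <1.5 - 1.0 x 10e9 /L". That fixes the scale on which 1500 is a usual white-cell threshold.
- Protocol 2.3 reports that blood eosinophil depletion lasted at least 1 month at 1 mg/kg "and for 3 months at all higher IV and SC doses".

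**The concern.** A withdrawal threshold should separate the unusual subject from the ordinary one. A rule about subjects who enter with high eosinophils, are depleted and then rebound needs a limit that is itself high. At 1.5 cells/µL the entry condition stops selecting high-eosinophil subjects and takes in nearly everyone. The rebound condition then describes the expected return of counts once the drug effect wears off. The Safety Monitor would have to disregard the printed unit or flag routine recovery. At stake is a clear safety instruction about who leaves the study, not the efficacy result.

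**Working it through.** The limit is a chosen threshold, not a derived figure, so there is no plan calculation to reproduce. The check is a unit conversion.

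**Inputs.** Printed limit 1500/mL (Protocol 14.11). Blood-cell scale 1500/mm3 = 1.5 × 10^9/L (Protocol Appendix 6). White-cell reporting step 0.01 × 10^9/L (SAP 5.1). Dose 300 mg, last double-blind dose Day 71, primary visit Day 85 (Protocol 5.1 and 7.2.1). Depletion of 3 months above 1 mg/kg (Protocol 2.3).

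**Step 1, convert the printed limit.**
- Per µL: 1500 ÷ 1000 = 1.5 cells/µL.
- In 10^9/L: 1500 × 1000 ÷ 10^9 = 0.0015.

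**Step 2, compare with Appendix 6.** Since 1 mm3 = 1 µL, 1500/mm3 is 1500/µL, or 1.5 × 10^9/L. The ratio is 1.5 ÷ 0.0015 = 1,000.

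**Step 3, compare with reporting precision.** One step of 0.01 × 10^9/L is 10/µL, or 10,000/mL, and 10,000 ÷ 1500 = 6.7. If eosinophils are reported in the same step, the smallest non-zero count is already 6.7 times the printed limit. This is an assumption: the SAP rule concerns the presentation of WBC and does not state laboratory resolution for eosinophils.

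**Step 4, try illustrative counts.** The documents give no eosinophil reference range.

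| Count per µL | Count per mL | Above 1500/mL? | Above 1500/µL? |
|---|---|---|---|
| 1 | 1,000 | no | no |
| 2 | 2,000 | yes | no |
| 50 | 50,000 | yes | no |
| 500 | 500,000 | yes | no |
| 1500 | 1,500,000 | yes | no |
| 1501 | 1,501,000 | yes | yes |

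Counts from 2 to 1500 per µL all pass the printed limit and fail the per-µL one. Step 4 does not depend on the assumption in Step 3.

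**Step 5, when recovery would occur.** 300 mg ÷ 1 mg/kg = 300 kg, so any subject under 300 kg receives more than 1 mg/kg. Day 85 is 85 − 71 = 14 days after the last dose, well inside 3 months. If the healthy-volunteer data carry over, most recovery falls after the Week 12 assessment.

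**The case against.** The strongest reply is that this is a probable typing error in a discretionary rule, and that a Safety Monitor reading absolute counts would see that 1.5/µL makes the entry condition pointless. That stands as to impact: two roles must act, and nobody is withdrawn automatically. It does not make the printed figure right.

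A text-extraction slip is also possible. The abbreviation list shows the microliter symbol intact, which makes a slip less likely but does not exclude it. If the source PDF shows µL, the unit point falls away.

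A reader might infer more than the documents support:

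- **Damage to the Week 12 analysis.** Early exit is an intercurrent event (Protocol 6, SAP 4.2.4), but Step 5 places most recovery after Week 12. A count of subjects wrongly withdrawn would need a probability of non-zero readings that the documents do not give.
- **Lost anti-drug-antibody data.** Protocol 12.3.6 and Table 1 note 16 still schedule samples 14 and 84 days after the last dose on early termination, and 15.2 encourages those who stop drug to complete follow-up.
- **Unblinding of the Medical Monitor.** Sections 4.4 and 8.6 require escalation that does not cause bias, and 11.3 and 12.1.10 withhold differentials from Sponsor and site. What exactly is passed on is operating detail that may sit in another document. Hiding the criterion from the role that must decide would be a debatable trade.
- **A conflict with Appendix 9.** When "eosinophil counts have not recovered by the OLE Day 155 visit (last follow-up visit), subjects will return approximately every 28 days", dosing is over and 15.1 already counts the OLE as completed. Section 20.9.7 does carry "AE reporting, withdrawal criteria and stopping rules, data collection and management" into the OLE, but a withdrawal at that stage changes nothing in practice.
- **A contradiction between the mandatory lead-in and the permissive bullet.** The first bullet also leaves the decision to judgement, and the specific wording is clear. This is editorial.

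**Conclusion.** The concern holds as a minor error. The text as supplied prints both the entry and the rebound limit at 1.5 cells/µL (0.0015 × 10^9/L), 1,000 times below the scale in Appendix 6. Read literally, the rule takes in almost any subject with detectable eosinophils and treats ordinary recovery as rebound. On the per-µL reading, only subjects entering above 1500/µL could qualify; the documents do not say how many there would be.

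The conclusion rests on two things: that the source PDF prints the unit as extracted, and, for the correction, that µL was intended, which is inferred from Appendix 6 and stated nowhere. The missing definition of initial suppression is a gap in detail and not a separate error.

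**What to change.** In Protocol 14.11, once the Sponsor has confirmed the intended unit and checked it against the source PDF, print the limit as >1500 cells/µL (1.5 × 10^9/L) in both places. Optionally, add a short clause giving the post-dose count or percentage fall that counts as initial suppression.

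The cost is one line, or two with the optional clause. The SAP, the schedule of visits and the data collected do not change.

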14.12 Study Stopping Rules

14.12.1 General

The study will be temporarily or permanently discontinued, and the DMC will convene for discussion of the case and for providing advice on study restart in the event of any of the following:

- An unexpected life-threatening AE that is confirmed to be related to treatment.
- A fatal AE that is confirmed to be related to treatment.
- Sponsor obtains new information leading to unfavorable risk-benefit judgment of the study drug.
- Sponsor's decision that continuation of the trial is unjustifiable for medical or ethical reasons.
- Discontinuation of development of the Sponsor's study drug.

The Sponsor reserves the right to close a trial site or terminate the trial at any time for any reason at the sole discretion of the Sponsor.

The Sponsor will notify all principal investigators outlining the reasons for the termination of the clinical trial. The Sponsor will provide principal investigators with instructions if assessments beyond the regular per protocol procedures should be necessary.

14.12.2 Additional Regional Stopping Rules

The study must be discontinued in the affected region in the event of any of the following events:

- Approval of the national competent authority or the Favorable Opinion/Approval of IEC/IRB for the conduct of the clinical trial is withdrawn.
- The required modification of the maximum insured sum is not possible following a negative change in the assessment of the benefit-risk ratio, if applicable.

Health Authorities and IEC/IRB will be informed about the discontinuation of the study in accordance with applicable regulations.

Study stopping for an individual site or investigator may occur in the event of noncompliance with the protocol or lapse of good clinical practice.

15. Discontinuation and Replacement of Subjects

15.1 Definition of Study Completion

A subject who completes visits through the Day 155 visit will be categorized as having completed the double-blind period of the study.

A subject who completes visits through the Day 85 visit and enters the OLE period of the study will be categorized as having completed the double-blind period of the study.

A subject who completes visits through the OLE Day 155 visit will be categorized as having completed the OLE period of the study.

The study is considered completed when the last subject completes the last study visit.

15.2 Early Discontinuation of Study Drug

A subject may be discontinued from study treatment at any time if the subject, the Investigator, or the Sponsor feels that it is not in the subject's best interest to continue. The following is a list of possible reasons for study treatment discontinuation:

- Subject withdraws consent.
- An AE that in the opinion of the Investigator results in it being in the best interest of the subject to discontinue study treatment.
- Protocol deviation requiring discontinuation of study treatment.
- Participation in any other study during the duration of this study.

- Use of a non-permitted concomitant drug, which may adversely affect data interpretation in the opinion of the Medical Monitor.
- Loss of ability to freely provide consent through imprisonment or involuntary incarceration or treatment of either a psychiatric or physical (e.g., infectious disease) illness.

If a subject is withdrawn from treatment due to an AE, the subject will be followed and treated by the Investigator until the abnormal parameter or symptom has resolved or stabilized.

All subjects who discontinue study drug treatment should be encouraged to continue on study and complete assessments and procedures according to the 12-week follow-up period in Table 1, if possible.

Reasonable attempts will be made by the Investigator to provide reasons for subject withdrawals. The reason for the subject's withdrawal from the study or all attempts to acquire such will be specified in the source documents.

16. Statistical Methods and General Considerations

This section outlines the statistical methods to be used for the analysis of the data from the study. A separate SAP, which must be documented as completed prior to unblinding the study, will describe data handling and statistical techniques in full detail.

When appropriate, summary statistics of number of non-missing values, mean, median, standard deviation, minimum, and maximum will be computed for continuous variables and summary statistics of number and proportion will be computed for categorical variables.

Two-sided 95% CI will be provided for the mean and proportion. No formal statistical inferences will be made for safety parameters. Safety data will be summarized for each treatment group unless otherwise specified.

Baseline for all safety and efficacy endpoints is defined as the last observations before administration of the first dose of study drug, unless otherwise specified.

Subjects will be stratified at randomization based on omalizumab experience for the treatment of CSU (exposed vs. naïve) and UAS7 score (16–27 vs. 28–42).

